6.6.3 Safety endpoints

From CTP Section 7.5: *With respect to safety evaluations, it is not planned to impute missing values.*

For safety data that are displayed by time point (or visit) of measurement, the OC-IR approach will be used. Observed cases including rescue (OC-IR) approach is an extension of the OC approach which includes all values which were measured both before and after any rescue medication intake. The analysis using OC-IR approach is only based on the patients with observed data.

The only exceptions where imputation might be necessary for safety evaluation are AE dates and start and stop dates for concomitant medications. Missing or incomplete AE dates are imputed according to BI standards (see 001-MCG-156_RD-01(7)).

[figure not shown]
Partial start and stop dates for concomitant medications and background, rescue, as well as historical medication for UC will be imputed to enable subsequent calculation (but not for display) by the following "worst case" approach:

- If the day of the end date is missing, then the end date is set to last day of the month (or to the patient's last contact date, if it is earlier than the last day of the month).
- If the day and month of the end date are missing then the end date is set to 31st of December of the year (or to the patient's last contact date, if it is earlier than the 31st of December of the year).
- If the day of the start date is missing the start date is set to first day of the month (except for rescue medication, where the day of first trial medication administration will be used if first dosing happened in the same month).

- If the day and month of the start date are missing then the start date is set to 1st January of the year (except for rescue medication, where the day/month of first trial medication administration will be used if first dosing happened in the same year).
- All other cases need to be assessed by the trial team on an individual basis, using the above points as guidance.

6.6.4 **PK data**

Missing data and outliers of PK data are handled according to BI standards (see 001-MCS-36-472_RD-01) ([8](#)).

6.6.6 **Time since first diagnosis**

For incomplete information on the date of first diagnosis, time since first diagnosis will be calculated as follows:

- If the year of first diagnosis is unknown, time since first diagnosis will be set to missing.
- If day and month of the first diagnosis are unknown, time since first diagnosis will be calculated as if diagnosed on the 30th June of that year.

- If only the day of the first diagnosis is unknown, time since first diagnosis will be calculated as if diagnosed on the 15th of that month.

6.7 BASELINE, TIME WINDOWS AND CALCULATED VISITS

Measurements reported with date and time and taken prior to start of administration of trial treatment will be considered pre-treatment values. Measurements reported with a date only (and no time) and taken on the day of first administration of trial treatment will also be considered pre-treatment values. These pre-treatment values will be assigned to visits according to the nominal visit number as recorded on the eCRF or as provided by the laboratory.

In addition, treatment-emergent adverse events which are reported with a date only (and no time) and which occur on the day preceding the first administration of trial treatment in the subsequent extension trial will be considered treatment-emergent AE in this parent trial.

Baseline, unless otherwise specified, is defined as the last measurement collected prior to the start of administration of the trial treatment.

Measurements taken after start of administration of trial treatment will be considered either on- or off-treatment values based on the definition in [Section 6.1](#), and will be assigned to visits for statistical analysis, if applicable, as defined below ([Table 6.7: 1](#)).

Analysis of AE data, concomitant medication or non-drug therapies, as well as use of rescue medication will not be based on visits. Therefore, no assignment to time windows will be necessary. Frequency tables for these data will be using on-treatment data only.

For derivation of the last value on treatment, minimum value on treatment, and maximum value on treatment, all on-treatment values (whether or not selected in any time window; see [Table 6.1: 1](#) for definition of the on-treatment period) will be considered; these will be derived for analysis of laboratory and vital signs data. For identification of potentially clinically significant abnormal laboratory values, all values (whether or not selected in any time window) within the on-treatment period will be considered.

Safety, efficacy and biomarker measurements will be assigned to visits based on extended time windows around the planned visit dates, defined relative to the day of first trial treatment (which is scheduled for Visit V2). These extended time windows are defined below in [Table 6.7: 1](#).

Table 6.7: 1 Time windows for assignment of efficacy, safety lab, vital signs and biomarker to visits for statistical analysis

Visit number /name	Visit label	Planned day	Time window (Days)				
			Window (per CTP)	Start (per CTP)	End (per CTP)	Start (extended)	End (extended)
V1a	Screening	-35 to -7	n/a				
V1b	Screening	- 28 to -7	n/a				
V2	Baseline	Day 1	+/- 0	1 ^A	1 ^A	≤1 ^A	1 ^A
On-treatment data only							
V3	Week 2	Day 15	+/- 4	11	19	2	22
V4	Week 4	Day 29	+/- 4	25	33	23	43
V5	Week 8	Day 57	+/- 4	53	61	44	71
EOT	Week 12/EoT	Day 85	+/- 4	81	89	72	Minimum of (cut-off, 99) ^C
All data (planned off-treatment data)							
Unscheduled	Unscheduled					100	148
EOS ^B	Week 24/EoS	Day 170	[contact]	Day of last f-up value

Days are counted relative to the day of first treatment, which is defined as Day 1.

^A Note that measurements made at Day 1 and assigned to the on-treatment period (because mistakenly made after start of infusion of trial treatment) via assessment on date and time (i.e. safety laboratory) will not be assigned to Day 1. Such data will be listed only.

^B Note that for patients rolling-over into open label trial 1368-0017, the analysis visit window of EOS should be the same as that of Week 12/EOT.

^C Cut-off date is not applicable for the final, updated trial analysis.

Repeated and unscheduled efficacy, safety and biomarker measurements will be handled similarly to scheduled measurements and will also be assigned to a time window depending upon the date of measurement.

Only one observation per time window will be selected for statistical analysis at a particular visit – the value which is closest to the protocol planned visit day will be selected. If there are two observations which have the same difference in days to the planned day, the later value will be selected. If there are two observations on the same day, the worst value will be selected.

Assignment of efficacy observations to visits based on time windows will be based on the non-imputed (observed) data.

For visits without an assigned value based on time windows, a value will thereafter be imputed as defined in Section 6.6. Imputation of efficacy endpoints, when applicable, will be performed based on all available observations obtained during the on-treatment period, irrespective of whether the observation was selected in any time window.

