**Footnotes:**

1. If disease extent has not been performed within past 12 months from screening, a full colonoscopy will be performed during screening period, instead of the screening and baseline sigmoidoscopy, to determine the extent of disease.
2. [REDACTED] At visits with study drug administration this should to be done prior to the study drug infusion. Colonoscopy and sigmoidoscopy images will be scored using the modified Mayo Endoscopy Score (mESS) recorded by the site investigator and centrally read by an external independent assessor(s); management of images will be performed by an external vendor.
3. Sigmoidoscopies will be performed at visit V1b if no colonoscopy is done.
4. Physical examination: C=complete, T=targeted. Refer to [Section 5.2.1](#). In addition, at Visits 2, 4 and 5 vital signs will be assessed at approximately 5 and 60 minutes after the end of study drug administration. Monitor for signs and symptoms of hypersensitivity reactions for approximately 2 hours after the first dose administered at Visit 2 and 1 hour following all other doses of study drug (at Visits 4 and 5).
5. Only applicable for women of childbearing potential. A serum pregnancy test will be performed at screening. Urine pregnancy tests will be performed at all other visits indicated in the [Flow chart](#). In case of a positive urine pregnancy test, a serum pregnancy test will be done. Urine pregnancy testing should be done prior to administration of study drug in case there is dosing at study visits. Study drug should only be administered in case of a negative test result. More frequent testing should be done if required by the local regulation and / or authority or per investigator judgment.
6. If collection is not possible at Visit 1a, stool sample has to be collected at (or prior to) Visit 1b or at an unscheduled visit.
7. Includes clinical chemistry, haematology, coagulation and urinalysis assessments. Patient must be fasting for at least 8 hours prior to blood collection (except screening visit). If not fasted mark on laboratory requisition form. At visits with study drug administration this should be done prior to the study drug infusion.
8. At study visits with study drug administration, pre-dose PK/ADA [REDACTED] samples will be obtained approximately within 1 hour prior to start of i.v. infusion.

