### 5.2.2 Vital signs

Vital signs evaluations will be performed at visits as shown in the [Flow Chart](#). This includes temperature, pulse rate, systolic/diastolic blood pressure and respiratory rate. Respiratory rate, pulse rate, and blood pressure will be measured after patients have been sitting comfortably for at least five minutes. Measurement of vital signs should precede blood sampling to avoid the impact of blood sampling on the vital measurements. At dosing visits (Visits 2, 4 and 5) vital signs evaluations will be performed pre-dose and additional evaluations will be taken approximately at 5 minutes post-dose and 60 minutes post-dose.

Patients should be closely monitored for signs and symptoms of hypersensitivity reactions for approximately 2 hours after the first dose administered and 1 hour following all other doses of study drug. Hypersensitivity reactions should be treated according to medical standards. Pre-medications for further injections might be considered and will be agreed on between investigator and BI clinical monitor.

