### Clinical monitoring after study drug administration:

The patient will be monitored for infusion reactions at the site for approximately 2 hours after after the end of first study drug infusion and 1 hour following all other doses of study drug. At all visits with study drug administration, vital signs will be assessed pre-dose, and at approximately 5 and 60 minutes after end of infusion.

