7.8.3 Vital signs

The analyses of vital signs (blood pressure, pulse rate, body temperature, and body weight, respiration rate) will be descriptive in nature.

Descriptive statistics of vital signs over time and for the difference from baseline (see [Section 6.7](#)) will be provided by treatment and will include the last value during on-treatment period, the minimum value during on-treatment period, and the maximum value during on-treatment period (see [Table 6.1: 1](#) for definition of the on-treatment period). Graphical displays via box

[figure not shown]
plots will be produced for the change from baseline, over time, for each continuous vital sign endpoint.

Clinically relevant findings in vital signs data will be reported as baseline conditions (at screening) or as AEs (during the trial) if judged clinically relevant by the investigator, and will be analysed as such.

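### Planned pre-dose and post-infusion vital signs at V4 and V5 are reduced to one undefined worst value per visit, and the SAP gives the V2 post-infusion readings no clear place in the by-visit tables

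*SAP*

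**What the plan says.** **Schedule.** Protocol Section 5.2.2 states: "At dosing visits (Visits 2, 4 and 5) vital signs evaluations will be performed pre-dose", and then that "additional evaluations will be taken approximately at 5 minutes post-dose and 60 minutes post-dose". Flow Chart footnote 4 and the clinical monitoring paragraph of Section 6.2.2 repeat this; the latter says "vital signs will be assessed pre-dose, and at approximately 5 and 60 minutes after end of infusion". V3 and V6 (Week 12/EOT) have no infusion and one planned reading each.

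**Visit assignment.** The title of SAP Table 6.7:1 lists vital signs among the data it governs. The extended windows are Day 2–22 for V3, 23–43 for V4, 44–71 for V5, and 72 to at most 99 for EOT. One value per window is analysed: the one nearest the planned day, or the later one if two are equally near. For values on one day, "If there are two observations on the same day, the worst value will be selected".

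**Day 1.** SAP Table 6.1:1 starts the on-treatment period at the date and time of the first infusion. Section 6.7 says that values with a date but no time "taken on the day of first administration of trial treatment will also be considered pre-treatment values". Baseline is the final value before dosing begins. Footnote A to Table 6.7:1 begins: "Note that measurements made at Day 1 and assigned to the on-treatment period (because mistakenly made after start of infusion of trial treatment". It goes on to name safety laboratory data, and says such values are not assigned to Day 1 and are only listed.

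**Summaries.** SAP Section 7.8.3 plans "Descriptive statistics of vital signs over time and for the difference from baseline", with a reference to Section 6.7, plus last, minimum and maximum on-treatment values. Section 6.7 builds those three from every on-treatment value, whether or not it was selected in a window.

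**The concern.** The selection rules are written for one value per visit, with occasional repeats. Vital signs at dosing visits are three planned readings with different purposes: the pre-dose one describes the patient's state at the visit, and the two later ones look for a reaction to the infusion. A rule that picks one of the three without regard to time point loses that distinction. The by-visit series then changes meaning from visit to visit: a single reading at V3 and EOT, but a selected extreme at V4 and V5, both set against a single pre-dose baseline.

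The stake is interpretive. Systemic hypersensitivity, including infusion reaction, is an adverse event of special interest, and monitoring is longest after the first infusion (about 2 hours, against 1 hour later). The tables as specified cannot show the change from before to after an infusion, and may show a rise or fall at V4 and V5 that comes from the selection rule alone.

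**Working it through.** The documents give no figure on this point, so there is nothing to reproduce. The check applies the SAP rules to the nine planned readings and then sizes the selection effect under stated assumptions.

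**Step 1: assign each reading, taking times as recorded**

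| Visit (planned day) | Pre-dose | +5 min | +60 min | By-visit result |
|---|---|---|---|---|
| V2 (Day 1) | V2/baseline | no window | no window | pre-dose value |
| V4 (Day 29) | V4 | V4 | V4 | worst of three |
| V5 (Day 57) | V5 | V5 | V5 | worst of three |

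At V2 the two later readings follow the start of infusion, so they are on-treatment, and the first on-treatment window opens on Day 2. This follows from the windows alone, without footnote A. Of nine planned readings, two have no by-visit slot and six collapse to two.

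If only dates are recorded, the V2 row changes: all three readings become pre-treatment values under the date-only rule in Section 6.7. The documents do not say whether vital signs carry a time.

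**Step 2: what worst means.** No direction is defined. For blood pressure, pulse, temperature and respiration rate, both high and low values can be abnormal, so two programmers could choose opposite readings from the same three.

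**Step 3: size of the selection effect, for illustration.** Assume three independent normal readings with equal mean and within-day SD *s*, no infusion effect, and worst meaning highest.

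- Expected maximum of three standard normals = 3/(2√π) = 3/(2 × 1.7725) = 0.846. A simulation of 2,000,000 triples gave 0.847.
- Expected excess over a single reading = 0.846 × *s*.
- Assumed systolic *s* of 4 mmHg: 0.846 × 4 = 3.4 mmHg. At 8 mmHg: 0.846 × 8 = 6.8 mmHg.
- Wider range: *s* of 3, 5 or 10 mmHg gives about 2.5, 4.2 or 8.5 mmHg.

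If worst means lowest, the shift has the same size and the opposite sign. Baseline is a single pre-dose value, so change from baseline at V4 and V5 carries the shift in full; V3 and EOT carry none. With the same *s* in every arm, the expected shift is the same in every arm.

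**Step 4: footnote A against the summary rule.** If the footnote were read to cover vital signs, its restriction to listings would conflict with the rule that all on-treatment values enter the last, minimum and maximum. The SAP does not say which prevails.

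**The case against.** **The same-day rule may be meant only for duplicates.** It speaks of two observations and follows a paragraph on repeated and unscheduled measurements. That reading is possible, but the rule has no such limit, and the table expressly covers vital signs. Taken literally, it does not address three readings at all, which leaves selection at V4 and V5 undefined.

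**Details may sit elsewhere.** The SAP refers technical implementation to an ADS plan and safety analyses to sponsor standards, neither of which is available. Time-point handling may be specified there. Against that, Section 7.8.2 cites guidance on repeat values at a visit for laboratory data, while the available text of Section 7.8.3 cites none for vital signs, and the general rule stands in the SAP.

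**The signal is not lost.** This stands. Extreme readings can still reach the minimum and maximum summaries, individual values are listed, clinically relevant findings become adverse events, and hypersensitivity has its own tables.

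**The numerical shift is only illustrative.** This also stands. The SD is assumed, the direction is assumed, no hypothesis test is involved, and the expected difference between arms is unbiased under those assumptions.

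**A stronger reading.** A reader might infer that footnote A removes all first-infusion vital signs, that is, up to 160 × 2 = 320 of 160 × 3 = 480 planned V2 sets. The documents do not support this. The footnote names safety laboratory data and concerns readings taken late by mistake; absence from the by-visit tables depends on readings being timed; the count assumes full enrolment, while the SAP records early termination; and the minimum and maximum rule draws on all on-treatment values.

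**Conclusion.** The V4 and V5 problem holds on the text. Three planned readings meet a rule that keeps one, chosen as worst with no direction defined, so by-visit values and changes from baseline at those visits mix time points and cannot be read alongside V3 and EOT. The illustrative shift of about 0.85 within-day SD rests on exchangeable readings and on worst meaning highest; the mmHg figures rest further on an assumed SD.

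The V2 problem is conditional. Timed post-infusion readings have no by-visit slot; dated-only readings would be classed as pre-treatment and could affect baseline, although the baseline definition itself would exclude a reading known to follow the infusion. The documents do not settle which applies.

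The effect is confined to descriptive by-visit safety tables. Efficacy, type I error and sample size are untouched. The point is worth correcting because the remedy is cheap.

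**What to change.** In SAP Sections 6.7 and 7.8.3:

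- use the pre-dose reading for baseline and for the by-visit series at V2, V4 and V5;
- exempt planned vital-sign time points from the same-day worst-value rule, and define the direction of worst for any true duplicates that remain;
- state whether vital signs are recorded with a time, and identify readings by planned time point so that V2 post-infusion values cannot be classed as pre-treatment;
- state that footnote A does not apply to planned vital signs, and reconcile its restriction to listings with the rule for last, minimum and maximum on-treatment values;
- summarise the 5- and 60-minute readings by planned time point, as change from pre-dose at each infusion, by arm.

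The cost is SAP wording and one extra descriptive table. The protocol already schedules every reading, so no further measurements are needed.

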7. PLANNED ANALYSIS

The following analyses are planned at different stages throughout Part 1 of this trial.

Part 1 – First Interim Database Snapshot - Week 12 Analysis

The analysis will be performed using all randomized patients who completed/ discontinued through the week 12 visit on or prior to the cut-off date (see Section 3). A database snapshot will then be done. At this time, an interim analysis of the efficacy and safety data through Week 12 will be performed by the sponsor.

The individual patient cut-off date for inclusion of data into the analysis is the minimum of the analysis-specific data cut-off, or study day 99, as described in [Table 6.7: 1](#).

The analyses as described in Section 6.3 of this TSAP will be performed using the subject sets of ESi, RSi, m-RSi, and SAFi.

Part 1 – Second Interim Database Snapshot - Week 12 Primary Analysis (All Randomized Patients)

The analysis will be performed using all randomized patients who completed/ discontinued through the week 12 visit. A database snapshot will then be done. At this time, the complete, primary analysis of all efficacy, safety, and PK/ADA data will be done through Week 12, and will be performed by the sponsor; biomarker data will be reported, if available.

The individual patient cut-off date for inclusion of data into the analysis is the minimum of the analysis-specific data cut-off, or study day 99, as described in [Table 6.7: 1](#).

The analyses as described in Section 6.3 of this TSAP will be performed using the subject sets of ES, RS, m-RS, SAF, and PPS.

Part 1 – Updated analysis after final DBL

A final database lock will be done when all randomized patients in Part 1 complete the trial. A majority of the trial patients are expected to roll-over into the extension trial at Week 12. The analyses as described in Section 6.3 of this TSAP will be performed, up to week 12, using the subject sets of ES, RS, m-RS, and SAF. Selected safety summaries including all data up to the REP, will also be generated.

General Remarks

The format of the listings and tables will follow the BI guideline "Reporting of clinical trials and project summaries" (001-MCG-159) ([9](#)).

The individual values of all patients will be listed, including those collected during the off treatment period. Listings will generally be sorted by country, centre number, patient number and visit (if visit is applicable in the respective listing). AE listings will be sorted by treatment (see [Section 7.8.1](#) for details).

The following standard descriptive statistical parameters will be displayed in summary tables for continuous variables:

N	number of non-missing observations
Mean	arithmetic mean
SD	standard deviation
Min	minimum
Q1	lower quartile
Median	median
Q3	upper quartile
Max	maximum

Statistical parameters will be displayed to a defined number of decimal places as specified in the BI guideline "Reporting of clinical trials and project summaries" (9).

Tabulations of frequencies for categorical data will include all possible categories and will display the number of observations in a category as well as the percentage (%) relative to the respective treatment group (unless otherwise specified, all patients in the respective patient set whether they have non-missing values or not). Percentages will be rounded to one decimal place. The category missing will be displayed only if there are actually missing values.

Due to the long REP, i.e., 16 weeks after last treatment, there will be no off-treatment data available at the time of the primary analysis at Week 12. Listings of data presented by-visit, which include both on- and off-treatment data, will be produced at the time of the updated analysis after final DBL (see also [Section 6.7](#)).

[figure not shown]
Disposition of the patient population participating in the trial will be summarised by presentation of the frequency of patients screened, entered, screened but not entered, treated, entered but not treated, who completed all doses of trial medication as planned, who completed the PE visit (EOT), who completed the trial (EOS), and who were prematurely discontinued, by reason. Disposition will also be summarized and listed by country. The frequency of patients with iPDs will be presented for the RS by treatment. The iPDs will be listed per patient indicating whether or not the iPD led to exclusion from patient sets analyzed.

The frequency of patients in each of the different analysis sets will also be presented by treatment.

All Section 7 analyses described below are presented for the second interim database snapshot (based on all randomized patients), using the subject sets of ES, RS, m-RS, SAF, and PPS. A sub-selection of these analyses will be performed at the time of the first interim database snapshot using the subject sets of ESi, RSi, m-RSi, and SAFi.

